2.8 Software

All analyses will be performed in either R v. 4.0.2 or later, or Stata v. 15 or later (College Station, TX: StataCorp LLC).

3. SUBJECT DISPOSITION

These summary metrics are descriptive in nature (not inferential). These measures will be reported both by treatment group (HD-TIV and SD-QIV) and overall.

- Absolute and relative frequency of participants randomized at each investigator site.
- The summary of subject disposition for all screened participants. This summary will include the number of participants screened, screen failure participants who were not randomized, participants who met all eligibility criteria and were not randomized, participants randomized, participants randomized but never treated, participants FAS, and participants in the SAS.
- The number and percentage of the participants in the following categories:
 - Completed study
 - Repeaters
 - Prematurely discontinued from study prior to the data cut date

4. DESCRIPTIVE ANALYSIS OF BASELINE CHARACTERISTICS

Summaries of baseline subject characteristics (overall, and by treatment group) will be provided using the Full Analysis Set. Baseline subject characteristics include the following:

- Subject demographic data (e.g., sex, race/ethnicity, age, social history).
- General clinical characteristics (body weight, height, body mass index, baseline titers).
- Disease characteristics (e.g., type of transplant, GVHD status)

Descriptive statistics on continuous data will be reported as (N, sample mean, sample standard deviation, median, interquartiles, minimum, and maximum); absolute and relative frequency will be used to describe categorical data. Of note, we will not perform formal hypothesis testing to compare these variables between treatment groups.

5. STATISTICAL ANALYSES FOR IMMUNOGENICITY OUTCOMES

This section presents plans for analysis corresponding to each of the primary, secondary, and tertiary objectives listed in Section 1.2.1. We utilize the following general notation to describe models of interest:

• i : indicator of subject• t : indicator of visit ($t = 2, t = 3$)• X : randomized group (0 = SD, 1 = HD)• Y : titer outcome	
• \mathbf{L} : pre-treatment covariates• γ_i : subject-specific random effect• γ_S : study site random effect• ε_{it} : error term
---	---

5.1 Analysis of continuous HAI titer responses

We will use mixed effect models to analyze continuous titers. All comparisons will be made on the geometric mean ratio scale. Consider the following model form:

$$\log(Y_{it}) = \beta_0 + \beta_1 \mathbf{1}(X = 1) + \beta_2 \mathbf{1}(t = 3) + \beta_3 \mathbf{1}(t = 3; X = 1) + \boldsymbol{\beta}_L \mathbf{L} + \gamma_i + \gamma_S + \varepsilon_{it},$$

under which all primary and secondary aims pertaining to continuous HAI titer outcomes can be addressed. The parameters of this model and the comparisons to which they correspond are summarized in Table 3.

Any continuous variables (e.g., time post-transplant and log-transformed baseline titer) used for adjustment will be flexibly modeled using natural cubic splines with knots at the 25th, 50th, and 75th percentiles.

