1.2 Study objectives

Immunogenicity and safety objectives are organized into subsections below. To avoid repetitive language, *all* objectives apply to the target study population (namely, pediatric HSCT recipients).

1.2.1 *Objectives for HAI immunogenicity outcomes*

The primary objective is to determine whether two doses of HD-TIV is associated with a higher geometric mean HAI titer to either influenza A antigen (H1N1 and H3N2, evaluated separately) compared to two doses of SD-QIV.

The secondary objectives pertaining to HAI immunogenicity outcomes are as follows:

- To determine whether two doses of HD-TIV is associated with a higher geometric mean HAI titer to influenza B antigens as compared to two doses of SD-QIV.
- To determine whether two doses of HD-TIV is associated with higher odds of seroconversion or seroprotection in *any* HAI antigen as compared to two doses of SD-QIV.
- To compare HAI immunogenicity for each antigen between the following groups: (a) one dose of HD-TIV vs. one dose of SD-QIV, (b) one dose of HD-TIV vs. two doses of HD-TIV, and (c) one dose of SD-QIV vs. two doses of SD-QIV.

The tertiary objectives pertaining to HAI immunogenicity outcomes are as follows:

- To compare HAI immunogenicity for each antigen between the one dose of HD-TIV and two doses of SD-QIV.
- To determine whether time post-transplant, subject age, or GVHD status (presence/absence) modifies the association between vaccination group and HAI response.
- To characterize the relationship between HAI titers, ex-vivo T and B cell phenotype, and ex-vivo influenza-specific T and B cell response in subjects receiving either HD-TIV or SD-QIV.
- To compare HAI immunogenicity outcomes between treatment groups (one dose or two doses of HD-TIV vs. one dose or two doses of SD-QIV, respectively) among those enrolled for a second year (repeaters).

1.2.2 *Objectives for safety outcomes*

The primary objectives for safety outcomes are to compare the frequency/severity of solicited local injection site adverse events (AEs) and systemic AEs between HD-TIV and SD-QIV following the first dose and following the second dose. The secondary objective is to compare safety outcomes between treatment groups among those enrolled for a second consecutive year (repeaters).

1.2.3 *Further exploratory objectives*

- To compare the persistence of HAI and microneutralization (MN) titers between HD-TIV and SD-QIV across all four antigens seven months after the final vaccine dose.

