8. TABLES

TABLE 1: STUDY SITES

#	Site
1	Vanderbilt University
2	Seattle Children's Hospital
3	Children's Hospital of Philadelphia (CHOP)
4	Children's Mercy Hospital
5	Cincinnati Children's Hospital
6	Nationwide Children's Hospital
7	St. Jude Children's Research Hospital
8	UCSF (University of California San Francisco) Benioff Children's Hospital
9	Baylor School of Medicine, Texas Children's Hospital

TABLE 2: DEFINITION OF ANALYSIS SETS

#	Analysis set	Description
1	All randomized (ARAS)	All participants randomized into the study, for use in by-subject listings.
2	Full (FAS)	All participants who (1) are randomized into the study and (2) have received at least 1 dose of either vaccine.
3	Safety (SAS)	All participants who (1) are randomized into the study and (2) have completed at least one memory aid.
4	Repeating (RAS)	All participants who are (1) randomized into the study and (2) received at least one vaccination as a repeater.

TABLE 3: PARAMETERS FOR MIXED MODEL OF INTEREST

#	Comparison	Visit	Comparison	Parameter	Null hypothesis	Classification
1	2 doses HD-TIV 2 doses SD-QIV	3 3	Between-group	$\exp(\beta_3)$	$H_0: \beta_3 = 0$	Primary
2	1 dose HD-TIV 1 dose SD-QIV	2 2	Between-group	$\exp(\beta_1)$	$H_0: \beta_1 = 0$	Secondary
3	1 dose SD-QIV 2 doses SD-QIV	2 3	Within SD-QIV	$\exp(\beta_2)$	$H_0: \beta_2 = 0$	Secondary
4	1 dose HD-TIV 2 doses HD-TIV	2 3	Within HD-TIV	$\exp(\beta_2 + \beta_3)$	$H_0: \beta_2 + \beta_3 = 0$	Secondary
5	1 dose HD-TIV 2 doses SD-QIV	2 3	Between-group	$\exp(\beta_2 - \beta_1)$	$H_0: \beta_2 - \beta_1 = 0$	Tertiary

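### SAP Table 3 ties the primary two-dose comparison to exp(β3), the visit-by-group interaction; under the Section 5.1 model the Visit 3 ratio of HD-TIV to SD-QIV is exp(β1+β3)

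*SAP*

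**What the plan says.** SAP Section 1.2.1 sets the target: the "primary objective is to determine whether two doses of HD-TIV is associated with a higher geometric mean HAI titer to either influenza A antigen", with H1N1 and H3N2 evaluated separately and two doses of SD-QIV as the comparator.

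SAP Section 5 codes X as 0 for SD and 1 for HD, and lets t take only the values 2 and 3, that is, after one dose and after two doses. Section 5.1 then gives the model

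log(Y) = β0 + β1·1(X=1) + β2·1(t=3) + β3·1(t=3; X=1) + covariates + subject and site random effects + error.

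It adds that "All comparisons will be made on the geometric mean ratio scale" and that "The parameters of this model and the comparisons to which they correspond are summarized in Table 3".

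Table 3 assigns the parameters as follows.

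| Row | Comparison | Parameter | Class |
|---|---|---|---|
| 1 | HD vs SD, Visit 3 | exp(β3) | Primary |
| 2 | HD vs SD, Visit 2 | exp(β1) | Secondary |
| 3 | Visit 3 vs Visit 2 within SD | exp(β2) | Secondary |
| 4 | Visit 3 vs Visit 2 within HD | exp(β2+β3) | Secondary |
| 5 | SD Visit 3 vs HD Visit 2 | exp(β2−β1) | Tertiary |

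**The concern.** The group term 1(X=1) is not restricted to Visit 2, so β1 applies to HD-TIV recipients at both visits, and β3 is what is added to it at Visit 3. Testing β3 = 0 asks whether the gap between arms changed after the second dose. The primary objective asks whether there is a gap after two doses.

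The two questions coincide only when β1 = 0, meaning no difference between arms after the first dose. The protocol's background gives no reason to expect that. In the dose-ranging study in older adults (Protocol B.3.a), mean HAI titers one month after vaccination were 61 with 60 µg and 37 with 15 µg for H1N1 (ratio 1.65), and 125 and 86 for H3N2 (ratio 1.45). Protocol B.2 also reports guidance that a second dose may add little. An early advantage that is then maintained is the pattern for which β3 is near zero.

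**Working it through.** **Step 1. Cell means from the Section 5.1 equation** (covariates and random effects held fixed).

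- SD, Visit 2: β0
- HD, Visit 2: β0 + β1
- SD, Visit 3: β0 + β2
- HD, Visit 3: β0 + β1 + β2 + β3

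**Step 2. Rebuild each row of Table 3.**

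- Row 2: (β0+β1) − β0 = β1. Agrees.
- Row 3: (β0+β2) − β0 = β2. Agrees.
- Row 4: (β0+β1+β2+β3) − (β0+β1) = β2+β3. Agrees.
- Row 5: (β0+β2) − (β0+β1) = β2−β1. Agrees.
- Row 1: (β0+β1+β2+β3) − (β0+β2) = **β1+β3**. The table gives β3. Does not agree.

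Rows 2, 3 and 4 on their own force the answer: the HD minus SD difference at Visit 3 is (β2+β3) + β1 − β2 = β1+β3.

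**Step 3. Could another coding rescue row 1?** If β1 acted only at Visit 2, row 1 would be β3 as printed. Row 4 would then be β2+β3−β1, which contradicts Table 3, and the group term in Section 5.1 would have to be written differently. Neither coding makes all five rows right, and under the printed one only row 1 fails.

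**Step 4. What row 1 would report.** Write GMR2 and GMR3 for the true HD/SD geometric mean ratios at Visits 2 and 3. Then exp(β3) = GMR3/GMR2 and exp(β1+β3) = GMR3.

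**Step 5. Rejection rates (illustrative).** Inputs:

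- 80 evaluable per arm, from 100 per arm and 20% dropout (Protocol 17.a)
- two-sided α = 0.05 (SAP 2.5)
- natural-log titer SD 1.5 and Visit 2 to Visit 3 correlation 0.7, both assumed because the documents give neither

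Standard errors:

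- Visit 3 contrast: 1.5·√(2/80) = 0.237
- β3: 1.5·√(2(1−0.7))·√(2/80) = 0.184

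Power is approximately Φ(|effect|/SE − 1.96).

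- GMR 2.0 at both visits. Visit 3 contrast: ln 2/0.237 = 2.92, so Φ(0.96) = 83%. β3: effect 0, so 5%.
- GMR 1.5 then 2.0. β3: ln(2/1.5)/0.184 = 1.57, so Φ(−0.39) = 35%.
- GMR 2.5 then 2.0. β3: |ln 0.8|/0.184 = 1.21, so Φ(−0.75) = 23%, with the estimate below 1.
- GMR 2.0 then 1.0. β3: |ln 0.5|/0.184 = 3.77, so Φ(1.81) = 96%.

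Simulated trials give the same picture (20,000 per scenario; 4,000 for the 2.5 then 2.0 row):

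| True GMR, Visit 2 then Visit 3 | exp(β3) | Rejects β3 = 0 | exp(β1+β3) | Rejects β1+β3 = 0 |
|---|---|---|---|---|
| 2.0, 2.0 | 1.00 | 4.9% | 2.00 | 83.0% |
| 1.5, 2.0 | 1.33 | 34.1% | 2.00 | 82.8% |
| 2.5, 2.0 | 0.80 | 23% | 2.00 | 84% |
| 2.0, 1.0 | 0.50 | 96.4% | 1.00 | 4.8% |

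**Step 6. Sensitivity to the assumed inputs.** Power of the correct contrast at GMR 2.0 is 99%, 83% and 59% for SDs of 1.0, 1.5 and 2.0. For GMR 1.5 then 2.0, the normal-approximation power of the β3 test runs from 15% (SD 2.0, correlation 0.5) to 82% (SD 1.0, correlation 0.8). When the two visit ratios are equal, the β3 test has only its 5% size for every SD and correlation.

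**The case against.** The strongest reply is that the intent is not in doubt. Section 1.2.1 states the objective clearly, and row 1's own labels (both arms at Visit 3, between-group, primary) describe the right comparison. An analyst who works from the labels would compute the right contrast, so this is a wrong entry in two cells and not a wrong model. That is fair as a description of the cause. It does not remove the problem: Section 5.1 names Table 3 as the place where parameters are matched to comparisons, both the parameter and the null-hypothesis cells of row 1 read β3 alone, and nothing elsewhere in the SAP corrects them. Loss in text extraction is unlikely, since the two-term expressions in rows 4 and 5 came through in both cells.

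Three further points stand and limit the claim.

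- With GMR 2.0 at both visits, the secondary row 2 would still show a ratio near 2.0 after one dose. The advantage would be missing from the primary result, not from the whole report.
- Carry-over to other sections is conditional. Sections 5.2, 5.3, 5.5 and 7.1 call for similar or analogous analyses, so they inherit the error only if Table 3 is followed literally. Section 5.4 does not name the coefficient to be modified. Section 7.2 uses Visit 4 as the outcome, so the Visit 2 to Visit 3 interaction does not transfer as written.
- The power figures leave out baseline-titer adjustment, site effects and imputation, and rest on an assumed SD and correlation.

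**Conclusion.** The concern holds. As written, the primary hypothesis test in Table 3 addresses the visit-by-group interaction and not the two-dose comparison in the primary objective. This is algebra on the SAP's own equation and needs no assumption about the data. exp(β3) equals the Visit 3 ratio divided by the Visit 2 ratio, so it understates the two-dose ratio whenever HD-TIV is already ahead after one dose, falls below 1 if that lead narrows, and can signal a difference when the arms are equal at Visit 3. With a true two-fold ratio at both visits, the primary result is centred on 1.0 with 5% rejection, against 2.0 and about 83% for the correct contrast (59% to 99% over the assumed SDs). Because it concerns the primary test, it should be corrected before the SAP is finalized and the data are unblinded; changing the primary hypothesis later would look post hoc.

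**What to change.** In Table 3 row 1, replace exp(β3) with exp(β1+β3), and the null β3 = 0 with β1+β3 = 0. Leave rows 2 to 5 and the Section 5.1 equation as they are. State that the confidence interval and Wald test for row 1 use the robust variance of the sum, Var(β1) + Var(β3) + 2Cov(β1, β3), consistent with Section 2.4.

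Add a short statement that the two-dose between-group contrast in Sections 5.2, 5.3, 5.5 and 7.1 is this same combination (an odds ratio where the link is logistic), and that Section 5.4 tests modification of the Visit 3 arm contrast. Section 7.2 should name its own Visit 4 arm contrast. β3 can stay as a descriptive interaction.

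The cost is one table row and a few clarifying sentences. The model, the data and the protocol's sample size, which rests on seroprotection proportions, are unaffected.

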5.2 Analysis of seroprotection

We will perform analyses similar to those of Section 5.1, instead using the binary indicator of *seroprotection* as the outcome, as defined by a titer of at least 1:40 to any of the four antigens. Correspondingly, we will utilize a logistic link instead of an identity link.

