**c. Pediatric Acute Lymphoblastic Leukemia (ALL) Subjects.** This single-center, randomized, double-blind, phase I safety and immunogenicity trial was conducted at Vanderbilt University, comparing HD to standard dose TIV in children 3-17 years of age with ALL. Fifty subjects were enrolled (20 in year 1 and 30 in year 2), with a mean age of 8.25 years, 62% were male, and 78% were receiving maintenance therapy. Thirty-four subjects were given HD and 16 were given standard dose. Safety data revealed no differences between the groups for total solicited systemic and local reactions; however, the standard dose group reported more fatigue and headache. No SAEs were attributed to vaccination. The immune response, measured by a  $\geq 4$ -fold rise in HAI titer, was similar for each vaccine antigen in both groups; however, descriptive data in ALL recipients comparing specific B-cell immune response to each antigen suggest better responses with HD-TIV (unpublished data, [name] laboratory, St. Jude, Memphis, TN). The main results are published in *Pediatric Blood Cancer*.

**5. Inclusion of Quadrivalent Inactivated Influenza Vaccine (QIV).** Although two influenza B lineages have been co-circulating since the 1980s, TIV contains only one B strain, which provides little-to-no protection against the alternate B-lineage strain; however, about 70% of recent B viruses have been antigenically related to the B virus component of the trivalent flu vaccines. A standard-dose QIV is currently available and provides additional protection against the second B strain while retaining non-inferior immunogenicity to the other 3 TIV strains. High dose QIV will not be available for the upcoming influenza season (*personal communication with Sanofi Pasteur*). This study will be the first to evaluate standard dose QIV and HD-TIV in this population.

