## Comparison of High vs. Standard Dose Flu Vaccine in Pediatric Stem Cell Transplant Recipients

DMID Protocol Number 16-0117

Protocol Version 8.0

Date: 9/12/2019

Since the majority of influenza illness is due to influenza A and HD-TIV licensure was based on influenza A antigen responses, the results of these studies could be generalizable to HD-QIV, should it become commercially available in the future. In addition, influenza B antigens have lower HAI titers compared to influenza A antigens, especially in children, including those without co-morbidities. Therefore, if the results from this trial reveal superior HAI titers to influenza A antigens, a HD-QIV vs. standard-dose QIV trial will not be necessary. Moreover, this study has significant potential to impact clinical practice in pediatric HSCT patients. Demonstration of safety and greater immunogenicity of HD-TIV versus standard dose QIV in this population could alter current influenza vaccine recommendations. Additionally, successful use of HD-TIV to enhance influenza-specific immune responses in pediatric HSCT patients could reduce influenza disease burden, morbidity, and mortality in these high-risk patients.

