**2. Primary and Secondary Study Objectives:****a. Primary Objectives:**

- To determine whether HD-TIV compared with standard dose IV will increase the probability of achieving a  $\geq 4$ -fold rise in HAI titers,  $\geq 1:40$  HAI titer, or higher GMT titers to influenza A antigens in pediatric HSCT recipients.

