**10. Investigational Product and Risk Information:**

Fluzone Quadrivalent® a Federal Drug Administration (FDA)-approved vaccine and is recommended for all pediatric patients  $\geq 6$  months.

Fluzone® HD-TIV has not yet been approved for individuals  $< 65$  years of age. The current seasonal influenza vaccine will be used for each study year (e.g. 2016-2017 or 2017-2018 or 2018-2019 or 2019-2020).

**a. Acquisition:** Fluzone Quadrivalent® and Fluzone® HD-TIV, preservative free, licensed product formulated for the 2016-2017 and/or 2017-2018 and/or 2018-2019 and/or 2019/2020 influenza season will be donated by Sanofi Pasteur and distributed to each site of the 9 institutions.

**b. Formulation, Packaging, and Labeling:** Fluzone Quadrivalent® and Fluzone® HD-TIV, preservative free, licensed product, Sanofi Pasteur, Swiftwater, PA. The 2016-2017 recommendations are the following: an A/California/7/2009 (H1N1)-like virus; an A/Hong Kong/4801/2014 (H3N2)-like virus; and a B/Brisbane/60/2008-like virus (this is a B/ Victoria lineage virus) in both products except in Fluzone Quadrivalent®, there is an additional B/Phuket/3073/2013-like virus (this is a B/ Yamagata lineage virus). The Fluzone package inserts for the 2016-2017 influenza season for both vaccines will be available in the Protocol Library.

Fluzone Quadrivalent® and Fluzone® HD, preservative free, licensed product formulated for the 2017-2018 influenza season, Sanofi Pasteur, Swiftwater, PA will be obtained. Formulation, Packaging, and Labeling: Fluzone Quadrivalent® and Fluzone® HD, preservative free, licensed product, Sanofi Pasteur, Swiftwater, PA. The 2017-2018 recommendations are the following: A/Michigan/45/2015 (H1N1)pdm09-like virus; an A/Hong Kong/4801/2014 (H3N2)-like virus; and a B/Brisbane/60/2008-like virus (this is a B/ Victoria lineage virus); and in Fluzone Quadrivalent®, additional B virus, B/Phuket/3073/2013-like virus, (this is a B/ Yamagata lineage virus). The Fluzone package inserts for the 2017-2018 influenza season for both vaccines will be available in the Protocol Library.

Fluzone Quadrivalent® and Fluzone® HD, preservative free, licensed product formulated for the 2018-2019 influenza season, Sanofi Pasteur, Swiftwater, PA will be obtained. Formulation, Packaging, and Labeling: Fluzone Quadrivalent® and Fluzone® HD, preservative free, licensed product, Sanofi

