## Comparison of High vs. Standard Dose Flu Vaccine in Pediatric Stem Cell Transplant Recipients

DMID Protocol Number 16-0117

Protocol Version 8.0

Date: 9/12/2019

Pasteur, Swiftwater, PA. The 2018-2019 recommendations are the following: A/Michigan/45/2015 (H1N1)pdm09-like virus; an A/Singapore/INFIMH-16-0019/2016 (H3N2)-like virus; and a B/Colorado/06/2017-like virus (this is a B/ Victoria lineage virus); and in Fluzone Quadrivalent®, additional B virus, B/Phuket/3073/2013-like virus, (this is a B/ Yamagata lineage virus). The Fluzone package inserts for the 2018-2019 influenza season for both vaccines will be available in the Protocol Library.

The 2019-2020 influenza strain recommendations are the following: A/Brisbane/02/2018 (H1N1)pdm09-like virus; A/Kansas/14/2017 (H3N2)-like virus; and B/Colorado/06/2017-like virus (B/Victoria/2/87 lineage) for both HD-TIV and SD-QIV; and in Fluzone Quadrivalent®, additional B virus, B/Phuket/3073/2013-like virus (B/Yamagata lineage). The Fluzone package inserts for the 2019-2020 influenza season for both vaccines will be available in the Protocol Library.

**c. Product Storage and Stability:** The vaccine will be stored in the original package to protect from light. The vaccine will be stored in secure, limited-access, temperature-monitored refrigerator environments at 2°C to 8°C (35.6°F to 46.4°F) until needed. The temperature of the storage unit will be monitored for the duration of the trial, and documentation of proper dedicated storage will be maintained. It will not be frozen. In the event of accidental deep-freezing or disruption of the cold chain, vaccines will not be administered.

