5.3 Analysis of seroconversion

We will perform analyses similar to those of Section 5.1, instead using the binary indicator of *seroconversion* as the outcome, as defined by at least a four-fold rise from baseline in titer within *any* of the four antigens. Correspondingly, we will utilize a logistic link instead of an identity link.

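### Seroprotection and seroconversion are scored on four antigens although HD-TIV contains three, so the HD-TIV vs SD-QIV odds ratio mixes antigen dose with strain presence and is pulled towards SD-QIV

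*SAP*

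**What the plan says.** SAP 5.2 defines seroprotection as "a titer of at least 1:40 to any of the four antigens". SAP 5.3 defines seroconversion as "at least a four-fold rise from baseline in titer within *any* of the four antigens". Both serve the secondary objective in SAP 1.2.1 on "higher odds of seroconversion or seroprotection in *any* HAI antigen", comparing two doses of HD-TIV with two doses of SD-QIV.

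Protocol C.10.b gives the strain content. For 2016-2017 the two products match, "except in Fluzone Quadrivalent®, there is an additional B/Phuket/3073/2013-like virus"; the entries for 2017-2018, 2018-2019 and 2019-2020 show the same pattern. Protocol C.15.b has HAI run for each antigen in QIV, so HD-TIV recipients are also tested against B/Yamagata. Protocol B.5 states that "TIV contains only one B strain, which provides little-to-no protection against the alternate B-lineage strain".

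The protocol's primary objective (C.2.a) names a four-fold rise, a titer of 1:40 or above, "or higher GMT titers to influenza A antigens in pediatric HSCT recipients"; influenza B is a separate secondary objective. The SAP's primary objective keeps only the influenza A GMT, with H1N1 and H3N2 evaluated separately.

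**The concern.** SD-QIV recipients have four vaccine-driven ways to count as responders and HD-TIV recipients have three. The trial asks whether more antigen improves response, and Protocol B.6 intends to carry the answer over to a high-dose quadrivalent product. An odds ratio that also reflects a missing strain does not answer that question.

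Two readings could go wrong. With no dose effect, the odds ratio is expected below 1 and could be taken as inferiority of the higher dose. With a true influenza A effect, it is diluted by the absent strain and by influenza B responses in general.

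The SAP names no two-dose HD-TIV vs SD-QIV contrast on either binary endpoint for influenza A or for the shared strains. Its per-antigen objective covers the one-dose comparison and the within-arm comparisons only. A null or reversed binary result would then stand beside the influenza A GMT ratios with no matching binary result to account for the difference.

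**Working it through.** **1. The plan's own figure.** Protocol C.17.a assumes 40% vs 20%, 80% power and 20% dropout. With two-sided alpha 0.05 (SAP 2.5) and unpooled variance, n per arm = (1.96 + 0.8416)² × (0.4×0.6 + 0.2×0.8) / 0.2² = 7.849 × 0.40 / 0.04 = 78.5. The protocol states 80, and 160/0.8 = 200. The figure is reproduced, and 80 per arm is used below.

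**2. Strain content, all four seasons.**

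| Antigen | HD-TIV | SD-QIV | Counts in SAP 5.2 and 5.3 |
|---|---|---|---|
| H1N1 | yes | yes | yes |
| H3N2 | yes | yes | yes |
| B/Victoria | yes | yes | yes |
| B/Yamagata | no | yes | yes |

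**3. Direction.** Take independent strains and no dose effect, and let Q be the probability of no response to any shared strain. The probability of non-response on all four is Q(1 − y_S) for SD-QIV and Q(1 − y_H) for HD-TIV, where y is the B/Yamagata response rate. The odds ratio is below 1 exactly when y_H < y_S, and equals 1 when they are equal.

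**4. Assumed inputs for size.** The documents give none of these: influenza A response 20% per strain; B strains 20% or 10% (Protocol B.6 says "influenza B antigens have lower HAI titers compared to influenza A antigens, especially in children"); B/Yamagata after HD-TIV 5%; correlation ρ between strains 0 to 0.5.

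Formulas:
- Independent strains: P(any) = 1 − ∏(1 − p_j).
- Correlated strains: P(any) = 1 − E_Z ∏Φ[−(t_j + √ρ Z)/√(1−ρ)], with t_j = Φ⁻¹(p_j) and Z standard normal.
- Test: Wald on the risk difference, two-sided 0.05, 80 per arm.

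**5. No dose effect.** Example with B at 20% and ρ = 0:
- SD-QIV: 1 − 0.8⁴ = 59.0%. HD-TIV: 1 − 0.8³×0.95 = 51.4%.
- OR = (0.5136/0.4864)/(0.5904/0.4096) = 0.73.
- z = −0.0768/√(0.5136×0.4864/80 + 0.5904×0.4096/80) = −0.98. The chance of a significant result favouring SD-QIV is Φ(0.98 − 1.96) = 16%.

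| B response | OR, ρ = 0 to 0.5 | Chance of a significant result favouring SD-QIV (should be 2.5%) |
|---|---|---|
| 20% | 0.73 to 0.82 | 16% to 9% |
| 10% | 0.89 to 0.93 | 5.5% to 4.0% |

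**6. HD-TIV doubles the influenza A response only (20% to 40%).** Power for ρ = 0 to 0.5:

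| Endpoint | B 20% | B 10% |
|---|---|---|
| Any of four | 45% to 47% | 79% to 76% |
| Any of the three shared strains | 84% to 74% | 91% to 85% |
| Either influenza A strain | 96% to 90% | 96% to 90% |

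The step from row 1 to row 2 is due to B/Yamagata. The step from row 2 to row 3 is ordinary dilution by B/Victoria.

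**7. Sensitivity of the no-effect odds ratio.**
- B/Yamagata after HD-TIV 2% to 10%, ρ up to 0.7: 0.69 to 0.95, and 1.00 where the B/Yamagata rates are equal in both arms. With a 0% rate after HD-TIV and B at 20%: 0.66 (ρ = 0) or 0.80 (ρ = 0.5).
- If 40% of both arms are at or above 1:40 whatever the vaccine (rate = 0.4 + 0.6p): 0.79 to 0.88 with B at 20%, 0.92 to 0.96 with B at 10%.
- If the SD-QIV any-of-four rate is set to 20%, following the sizing sentence in C.17.a, with B equal to or half of A and B/Yamagata after HD-TIV at 25% or 50% of its SD-QIV rate: 0.79 to 0.93, with a 4% to 8% chance of a significant result favouring SD-QIV.

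**The case against.** **The wording might mean each antigen.** SAP 5.2 and 5.3 follow 5.1, which serves per-antigen GMT objectives. If the per-antigen objective covers the binary endpoints, the models fitted for it would also yield a two-dose influenza A contrast. But SAP 1.2.1 uses *any* and *each antigen* for different objectives, and 5.2 and 5.3 define only the four-antigen form. As written it is a composite. If separate analyses were meant, the text still needs correcting.

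**The comparison is between products.** For that question the missing B strain is part of HD-TIV's real effect. This is a legitimate question, but it is not the dose question in the hypotheses or in the planned extrapolation to a quadrivalent high-dose vaccine. The SAP does not say that it chose the product question.

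**The size is soft.** This stands. The protocol's remark on TIV concerns protection rather than HAI titer, and the 5% rate is assumed. The 45% to 47% power also gives HD-TIV no effect on B/Victoria. If B/Victoria doubles as well (B 20%, ρ = 0), HD-TIV is 1 − 0.6³×0.95 = 79.5% against 59.0%, and power is about 82%.

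**The test modelled is simpler than the SAP's.** The SAP uses an adjusted mixed logistic model with multiple imputation. SAP Table 3 also attaches the two-dose contrast to β3, an interaction, in which a pull present at both visits would partly cancel. The figures above are for the visit 3 odds ratio, which is what the objective asks for.

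**A B/Yamagata deficit would be visible elsewhere.** GMT ratios for the B antigens are planned, so it would show there. They would not supply the missing influenza A or shared-strain binary result.

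**Conclusion.** The point holds and should be corrected. SAP 5.2 and 5.3 score both arms on a strain that only one arm receives, and nothing in either document restricts the composite to shared strains or acknowledges the imbalance. The direction requires only that B/Yamagata responses be lower after HD-TIV, which Protocol B.5 leads one to expect. The pull vanishes if the rates are equal, and background or immunoglobulin-derived antibody weakens it, mainly for seroprotection.

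The size is illustrative: across the sensitivity cases with unequal B/Yamagata rates, the odds ratio with no dose effect runs from 0.66 to 0.96. The loss of power ranges from modest to severe, depending on the influenza B rates and on whether HD-TIV also raises B/Victoria responses. The primary influenza A GMT analysis and the one- vs two-dose comparisons within an arm are not affected.

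**What to change.** In SAP 5.2 and 5.3, and in the matching objective in 1.2.1:

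- Analyse the two-dose HD-TIV vs SD-QIV contrast for both binary endpoints by antigen, with H1N1 and H3N2 as the key ones. Since this adds contrasts at a nominal 0.05, state how multiplicity is handled or label the remaining contrasts as supportive.
- Restrict any composite to H1N1, H3N2 and B/Victoria.
- Report B/Yamagata separately, as strain present vs strain absent, not as a dose effect.
- Record that the sizing sentence in Protocol C.17.a refers to at least one influenza antigen while its table rows are labelled strain A, and say which endpoint the 80% power refers to.

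The cost is SAP wording and a few more models on HAI titers already measured per antigen. SAP 1.3 puts the unblinded analyses after the SAP is final, so the change belongs before that point.
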